7.7 Transverse myelitis	

Definition: Acute or subacute weakness or sensory changes bilateral, often with increased deep tendon reflexes
	

Diagnostic work-up
 
Neurologic consultation
 
MRI of spine (with thin axial cuts through the region of suspected abnormality) and MRI of brain
 
Lumbar puncture: cell count, protein, glucose, oligoclonal bands, viral PCRs, cytology, onconeural antibodies
 
Blood: B12, HIV, RPR, ANA, Ro/La, TSH, aquaporin-4 IgG
 
Evaluation for urinary retention, constipation
	
Grading	Management

G1: Mild, no interference with function and symptoms not concerning to patient. Note: Any cranial nerve problem should be managed as moderate.
 
G2: Moderate, some interference with ADL, symptoms concerning to patient (ie, pain but no weakness or gait limitation)
 
G3-4: Severe, limiting self-care and aids warranted
	
Permanently discontinue ICPi
 
Methylprednisolone 2 mg/kg
 
Strongly consider higher doses of 1 g/d for 3-5 days
 
Strongly consider IVIG

All recommendations are expert consensus based, with benefits outweighing harms, and strength of recommendations are moderate.
	

Abbreviations: AChR, acetylcholine receptor; ACTH, adrenocorticotropic hormone; ADL, activities of daily living; ANCA, antineutrophil cytoplasmic antibodies; CPK, creatine phosphokinase; CRP, C-reactive protein; EMG, electromyography; ESR, erythrocyte sedimentation rate; HSV, herpes simplex virus; ICPi, immune checkpoint inhibitor; ICU, intensive care unit; IgG, immunoglobulin G; IV, intravenous; IVIG, intravenous immunoglobulin; irAE, immune-related adverse event; MGFA, Myasthenia Gravis Foundation of America; MRI, magnetic resonance imaging; NA, not applicable; NCS, nerve conduction study; NIF, negative inspiratory force; PCR, polymerase chain reaction; RPR, rapid plasma reagin; TPO, thyroid peroxidase; TSH, thyroid-stimulating hormone; TTE, transthoracic echocardiogram; VC, vital capacity.
	

Table 8. Management of Hematologic irAEs in Patients Treated With ICPIs	
8.0 Hematologic Toxicities	
8.1 Autoimmune hemolytic anemia	
Definition: A condition in which RBCs are destroyed and removed from the blood stream before their normal lifespan is over. Symptoms include weakness, paleness, jaundice, dark-colored urine, fever, inability to do physical activity, and heart murmur.	
Diagnostic work-up	
History and physical examination (with special consideration of history of new drugs and insect, spider, or snake bites)	
Blood chemistry, CBC with evidence of anemia, macrocytosis, evidence of hemolysis on peripheral smear; LDH, haptoglobin, bilirubin, reticulocyte count, free Hgb DIC panel, which could include PTINR infectious causes	
Autoimmune serology	
Paroxysmal nocturnal hemoglobinuria screening	
Direct and indirect bilirubin; LDH; direct agglutinin test; and if no obvious cause, bone marrow analysis, cytogenetic analysis to evaluate for myelodysplastic syndromes	
Evaluation for viral/bacterial (mycoplasma, etc) causes of hemolysis studies	
Protein electrophoresis, cryoglobulin analysis	
Work-up for bone marrow failure syndrome if refractory, including B12, folate, copper, parvovirus, FE, thyroid, infection	
Glucose-6-phosphate dehydrogenase	
Evaluation of common drug causes (ribavirin, rifampin, dapsone, interferon, cephalosporins, penicillins, NSAIDs, quinine/quinidine, fludarabine, ciprofloxacin, lorazepam, diclofenac, etc)	
Assessment of methemoglobinemia	
Grading	Management
G1: Hgb < LLN to 10.0 g/dL; < LLN to 6.2 mmol/L; < LLN to 100 g/L	Continue ICPI with close clinical follow-up and laboratory evaluation
G2: Hgb < 10.0 to 8.0 g/dL; < 6.2 to 4.9 mmol/L; < 100 to 80 g/L	Hold ICPI and strongly consider permanent discontinuation Administer 0.5-1 mg/kg/d prednisone equivalents
G3: Hgb < 8.0 g/dL; < 4.9 mmol/L; < 80 g/L; transfusion indicated	Permanently discontinue ICPI Should use clinical judgment and consider admitting the patient Hematology consult Prednisone 1-2 mg/kg/d (oral or IV depending on symptoms/speed of development) If worsening or no improvement, 1-2 mg/kg/d prednisone equivalents and permanently discontinue ICPI treatment Consider RBC transfusion per existing guidelines; do not transfuse more than the minimum number of RBC units necessary to relieve symptoms of anemia or to return a patient to a safe Hgb range (7-8 g/dL in stable, noncardiac inpatients) Should offer patients supplementation with folic acid 1 mg once daily
G4: Life-threatening consequences, urgent intervention indicated	Permanently discontinue ICPI Admit patient Hematology consult IV prednisone corticosteroids 1-2 mg/kg/d If no improvement or if worsening while on corticosteroids or severe symptoms on presentation, initiate other immunosuppressive drugs, such as rituximab, IVIG, cyclosporin A, and mycophenolate mofetil RBC transfusion per existing guidelines; discuss with blood bank team prior to transfusions that a patient with possible ICPI serious AE is in house.
Additional considerations: Monitor Hgb levels on a weekly basis until the corticosteroid tapering process is complete; thereafter, less-frequent testing is needed ^{16,4}	
8.2 Acquired TTP	
Definition: A disorder characterized by the presence of microangiopathic hemolytic anemia, thrombocytopenic purpura, fever, renal abnormalities, and neurologic abnormalities, such as seizures, hemiplegia, and visual disturbances. It is an acute or subacute condition.	
Diagnostic work-up	
History with specific questions related to drug exposure (eg, chemotherapy, sirolimus, tacrolimus, opana ER antibiotics, quinine)	
Physical examination, peripheral smear	
ADAMTS13 activity level and inhibitor titer	
LDH, haptoglobin, reticulocyte count, bilirubin, urinalysis to rule out other causes	
PT, activated PTT, fibrinogen	
Blood group and antibody screen, direct antiglobulin test, CMV serology	
Consider CT/MRI brain, echocardiogram, ECG	
Viral studies	
Note: This disorder is usually associated with a severe drop in platelets and hemolysis/anemia precipitously	
Grading	Management
All grades	The first step in the management of TTP is a high index of suspicion for the diagnosis and timely recognition; hematology consult should immediately be called, as delay in identification is associated with increased mortality/morbidity. Initially, the patient should be stabilized and any critical organ dysfunction stabilized
G1: Evidence of RBC destruction (schistocytosis) without anemia, renal insufficiency, or thrombocytopenia clinically	Hold ICPI and discuss resumption with patient only after taking into account the risks and benefits, noting that there are currently no data to recommend restarting ICPI therapy
G2: Evidence of RBC destruction (schistocytosis) without clinical consequence with G2 anemia and thrombocytopenia	Hematology consult Administer 0.5-1 mg/kg/d prednisone
(continued on following page)	

Table 8. Management of Hematologic irAEs in Patients Treated With ICPi (continued)	
8.0 Hematologic Toxicities	
G3: Laboratory findings with clinical consequences (G3 thrombocytopenia, anemia, renal insufficiency > 2)	Hold ICPi and discuss resumption with patient only after taking into account the risks and benefits, noting that there are currently no data to recommend restarting ICPi therapy
G4: Life-threatening consequences (eg, CNS hemorrhage or thrombosis/embolism or renal failure)	Hematology consult In conjunction with hematology, initiate PEX according to existing guidelines with further PEX dependent on clinical progress ⁹⁴⁻⁹⁶ Administer methylprednisolone 1 g IV daily for 3 days, with the first dose typically administered immediately after the first PEX May offer rituximab
8.3 Hemolytic uremic syndrome	
Definition: A disorder characterized by a form of thrombotic microangiopathy with renal failure, hemolytic anemia, and severe thrombocytopenia. Signs and symptoms of hemolytic uremic syndrome can include:	

 Bloody diarrhea Decreased urination or blood in the urine Abdominal pain, vomiting, and occasionally fever Pallor Small, unexplained bruises or bleeding from the nose and mouth Fatigue and irritability Confusion or seizures High blood pressure Swelling of the face, hands, feet, or entire body 	
Diagnostic work-up	

 History and physical examination (special consideration for new history of high-risk drugs, hypertension, or cardiac causes) CBC with indices Blood smear morphology. Note that the presence of schistocytes on smear is critical for diagnosis. Serum creatinine ADAMTS13 (to rule out TTP) Homocysteine/methylmalonic acid Complement testing C3, C4, CH50 (complement inhibitory antibodies for suspected familial) Evaluate reticulocyte count and mean corpuscular volume Evaluation of infectious cause, including screening for EBV, CMV, HHV6 Evaluation for nutritional causes of macrocytosis (B12 and folate) Pancreatic enzymes Evaluation for diarrheal causes, shiga toxin, Escherichia coli 0157, etc Direct antibody test (Coombs test), haptoglobin, LDH, and other etiologies of anemia Evaluation for common drugs causing hemolysis (tacrolimus, cyclosporine, sirolimus, etc) Evaluation for concurrent confusion 	
Grading	Management
G1-2: Evidence of RBC destruction (schistocytosis) without clinical consequences of anemia, thrombocytopenia grade 2	Continue ICPi with close clinical follow-up and laboratory evaluation Supportive care
G3: Laboratory findings with clinical consequences (eg, renal insufficiency, petechiae)	Permanently discontinue ICPi Begin therapy with eculizumab therapy 900 mg weekly for four doses, 1,200 mg week 5, then 1,200 mg every 2 weeks
G4: Life-threatening consequences (eg, CNS thrombosis/embolism or renal failure)	Red blood transfusion according to existing guidelines
8.4 Aplastic anemia	
Definition: Condition in which the body stops producing enough new blood cells	
Diagnostic work-up	

 History and physical examination (close attention to medications, exposure to radiation, toxins, recent viral infections) CBC, smear, reticulocyte count Viral studies, including CMV, HHV6, EBV, parvovirus Nutritional assessments including B12, folate, iron, copper, ceruloplasmin, vitamin D Serum LDH, renal function Work-up for infectious causes Identify marrow hypo/aplasia Bone marrow biopsy and aspirate analysis Peripheral blood analysis, including neutrophil count, proportion of GPI-negative cells by flow for PNH Flow cytometry to evaluate loss of GPI-anchored proteins Type and screen patient for transfusions and notify blood bank that all transfusions need to be irradiated and filtered 	
Grading	Management
G1: Nonsevere, > 0.5 polymorphonuclear cells × 10 ⁹ /L hypocellular marrow, with marrow cellularity < 25%, peripheral platelet count > 20,000, reticulocyte count > 20,000	Hold ICPi and provide growth factor support and close clinical follow-up, and laboratory evaluation Supportive transfusions as per local guidelines
G2: Severe, hypocellular marrow < 25% and two of the following: ANC < 500, peripheral platelet < 20,000, and reticulocyte < 20,000	Hold ICPi and provide growth factor support and close clinical laboratory evaluations daily Administer ATG + cyclosporine; HLA typing and evaluation for bone marrow transplantation if patient is candidate; all blood products should be irradiated and filtered Supportive care with granulocyte colony-stimulating factor may be added in addition
(continued on following page)	

Table 8. Management of Hematologic irAEs in Patients Treated With ICPIs (continued)	
8.0 Hematologic Toxicities	
G3-4: Very severe, ANC < 200, platelet count < 20,000, reticulocyte count < 20,000, plus hypocellular marrow < 25%	Hold ICPI and monitor weekly for improvement; if not resolved, discontinue treatment until AE has reverted to G1 Hematology consult, growth factor support Horse ATG plus cyclosporine If no response, repeat immunosuppression with rabbit ATG plus cyclosporine, cyclophosphamide For refractory patients, consider eltrombopag plus supportive care
8.5 Lymphopenia	
Definition: An abnormally low level of lymphocytes in PB; for adults, counts of < 1,500/mm ³	
Diagnostic work-up	
History and physical examination (special attention for lymphocyte-depleting therapy such as fludarabine, ATG, corticosteroids, cytotoxic chemotherapy, radiation exposure, etc, as well as history of autoimmune disease, family history of autoimmune disease)	
Evaluation of nutritional state as cause	
Spleen size	
CBC with differential, peripheral smear and reticulocyte counts	
CXR for evaluation of presence of thymoma	
Bacterial cultures and evaluation for infection (fungal, viral, bacterial specifically CMV/HIV)	
Grading	Management
G1-2: 500-1,000 PB lymphocyte count	Continue ICPI
G3: 250-499 PB lymphocyte count	Continue ICPI, checking CBC weekly for monitoring, initiation of CMV screening
G4: < 250 PB lymphocyte count	Consider holding ICPI Initiate Mycobacterium avium complex prophylaxis and Pneumocystis jirovecii prophylaxis, CMV screening, HIV/hepatitis screening if not already done May consider EBV testing if evidence of lymphadenopathy/hepatitis, fevers, hemolysis consistent with lymphoproliferative disease
8.6 Immune thrombocytopenia	
Definition: An autoimmune disorder characterized by immunologic destruction of otherwise normal platelets	
Diagnostic work-up	
History and physical examination (special attention for lymphocyte-depleting therapy, such as fludarabine, ATG, corticosteroids, cytotoxic therapy)	
Family history of autoimmunity or personal history of autoimmune disease	
History of viral illness	
CBC	
Peripheral blood smear, reticulocyte count	
Bone marrow evaluation only if abnormalities in the above test results and further investigation is necessary for a diagnosis	
Patients with newly diagnosed immune thrombocytopenia should undergo testing for HIV, hepatitis C virus, hepatitis B virus, and Helicobacter pylori	
Direct antigen test should be checked to rule out concurrent Evan syndrome	
Nutritional evaluation	
Bone marrow evaluation if other cell lines affected and concern for aplastic anemia	
Grading	Management
G1: Platelet count < 100/ μ L	Continue ICPI with close clinical follow up and laboratory evaluation
G2: Platelet count < 75/ μ L	Hold ICPI but monitor for improvement; if not resolved, interrupt treatment until AE has reverted to G1 Administer prednisone 1 mg/kg/d (dosage range, 0.5-2 mg/kg/d) orally for 2-4 weeks after which time this medication should be tapered over 4-6 weeks to the lowest effective dose IVIg may be used in conjunction with corticosteroids if a more-rapid increase in platelet count is required.
G3: Platelet count < 50/ μ L	Hold ICPI but monitor for improvement; if not resolved, interrupt treatment until AE has reverted to G1
G4: Platelet count < 25/ μ L	Hematology consult Prednisone 1-2 mg/kg/d (oral or IV depending on symptoms) If worsening or no improvement, 1-2 mg/kg/d prednisone equivalents and permanently discontinue treatment IVIg used with corticosteroids when a more-rapid increase in platelet count is required If IVIG is used, the dose should initially be 1 g/kg as a one-time dose. This dosage may be repeated if necessary If previous treatment with corticosteroids and/or IVIG unsuccessful, subsequent treatment may include rituximab, thrombopoietin receptor agonists, or more-potent immunosuppression (From American Society of Hematology guideline on immune thrombocytopenia ³⁷ ; consult for further details)

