and described in detail in **Appendix 1** with specific application to this protocol. These recommendations include management of the toxicity itself, as well as guidance for dose interruptions/delays of the investigational agents. There are no dose reductions or dose escalations permitted for either investigational agent.

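### Appendix 1 items 8.6 and 8.4 print platelet limits on incompatible scales, so the temporary study-drug hold for immune thrombocytopenia, read literally, would not trigger at counts that 8.4 already treats as severe

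*Combined protocol and SAP*

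**What the plan says.** Item 8.6 (Immune thrombocytopenia) in Appendix 1 sets four grades by platelet count, each followed by a per-microlitre unit: "G1: Platelet count < 100", "G2: Platelet count < 75", "G3: Platelet count < 50" and "G4: Platelet count < 25". Study drug continues at Grade 1. From Grade 2 the instruction is "Hold ICPI but monitor for improvement; if not resolved, interrupt treatment until AE has reverted to G1".

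Item 8.4 (Aplastic anemia), two items earlier in the same table, describes Grade 1 with "peripheral platelet count > 20,000, reticulocyte count > 20,000". Its Grade 2 and Grade 3-4 rows use a platelet count below 20,000. No unit is printed beside these platelet figures.

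Section 5.8.1 says that Appendix 1 applies to this protocol and supplies "guidance for dose interruptions/delays of the investigational agents". The note at the head of Appendix 1 says that its abbreviation for checkpoint inhibitor means both study drugs here, and that the tables were copied from a published guideline.

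Two other sections bear on the point. Section 9.1.1 names CTCAE v5.0 as the severity scale for adverse events. Section 5.7 requires both drugs to be stopped permanently for a Grade 4 immune-related event (except an endocrinopathy controlled by hormone replacement). Subject to listed exceptions, it also requires this for a possibly drug-related toxicity of CTCAE Grade 2 or higher that does not improve to Grade 1 within 12 weeks of the last dose.

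**The concern.** Two items in one table use platelet counts as decision limits, and they differ by more than two orders of magnitude. Some difference is expected, because the items concern different diseases, but they cannot both be on a per-microlitre scale as printed. A count of 20,000, which 8.4 uses to separate its mildest grade from its severe one, is far above the upper limit of Grade 1 in 8.6.

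These cells are working text. Platelets are part of the hematology panel in Table 12, and blood counts are scheduled throughout treatment in Tables 8 and 9, so results will arrive that have to be compared with a rule. Item 8.6 is the only place in the documents that gives numerical platelet limits for holding study drug in immune thrombocytopenia. Someone applying it literally would keep dosing at counts that the same appendix calls severe under another heading.

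**Working it through.** No sample size, power or error rate is involved. The check concerns units and ratios.

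**Inputs**
- Item 8.6: platelet limits of 100 (G1), 75 (G2), 50 (G3) and 25 (G4) per microlitre.
- Item 8.4: platelet limit of 20,000, no unit printed. Neutrophil limits of 0.5 × 10^9/L in the Grade 1 row and 500 in the Grade 2 row.
- Item 8.5 (Lymphopenia), which lies between them: lymphocyte count below 1,500/mm³.

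**Step 1: the unit in 8.4.** One litre is 10^6 microlitres, so 0.5 × 10^9/L = 0.5 × 10^9 / 10^6 = 500 per microlitre. This equals the unitless neutrophil figure of 500 in the next row. The unitless counts in 8.4 are therefore per microlitre, and its platelet cut-off is 20,000 per microlitre. Item 8.5 also uses whole counts, since 1 mm³ is 1 microlitre.

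**Step 2: the ratio of the 8.4 cut-off to each 8.6 limit as printed.**

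| Grade in 8.6 | Printed limit (per microlitre) | 20,000 / limit |
|---|---|---|
| G1 (continue) | 100 | 200 |
| G2 (first hold) | 75 | 267 |
| G3 | 50 | 400 |
| G4 | 25 | 800 |

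A count of 20,000 per microlitre is 200 times the Grade 1 limit, so it would be ungraded under 8.6. It would have to fall by a further factor of about 267 before the first hold applied.

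**Step 3: would a missing factor of 1,000 explain the gap?** Multiplying the four limits by 1,000 gives 100,000, 75,000, 50,000 and 25,000. Divided by 20,000, these are 5, 3.75, 2.5 and 1.25. The two items would then lie on one scale, within a factor of five. This shows only that a dropped multiplier is a plausible cause. It does not establish what the limits should be.

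**The case against.** The strongest reply has four parts.

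**Other rules cover the toxicity.** This largely stands for permanent stopping. Section 5.7 stops both drugs for a Grade 4 immune-related event and for unresolved CTCAE Grade 2 or higher toxicity. It also requires a stop when the investigator or Medical Director judges that a drug-related event makes continuing contrary to the subject's interest. Section 5.8.1 asks for immediate discussion of any immune-related event of Grade 2 or higher with the principal investigator. None of these uses the numbers in 8.6. However, none of them gives the platelet count at which to hold drug in the meantime, and that is what 8.6 is for. The backstop is partial.

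**Items 8.4 and 8.6 grade different diseases.** This is true. The severe grade in 8.4 also needs a hypocellular marrow and two of three low counts, so the cut-offs need not coincide. That accounts for a modest difference, not for a factor of 200 to 800.

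**The table is copied guideline material, and a character may have been lost in reading the PDF.** Copying explains where the text came from, but the protocol adopts it as its own guidance. A reading fault cannot be excluded, because other cells in the appendix text show damage. It is less likely here: all four rows have the same form, and nearby notation such as 10^9/L and mm³ is intact.

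**Clinicians will read the figures as thousands.** Many probably will. This lowers the practical risk, but a numerical rule that is safe only when staff silently correct it still needs correcting.

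Several stronger conclusions are tempting and are not supported:
- A reader might infer that 8.6 contradicts CTCAE v5.0 platelet grading. The documents give no CTCAE platelet cut-offs; Table 14 has only generic descriptions. All that can be said is that the two must be reconciled.
- A reader might infer that the Grade 4 stop in 5.7, the safety run-in count in 3.1 or the tables of immune-related events in 8.2.2 are compromised. The run-in uses the 5.7 criteria and severity is graded under 9.1.1, so a dependence on 8.6 is not shown.
- A reader might describe the printed gap as 1,000-fold, or the limits as unreachable. The computed ratios are 200 to 800, the 1,000 is an inferred scale factor, and a count below 75 per microlitre is not arithmetically impossible.

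**Conclusion.** The inconsistency is real and shows from the protocol's own text. As printed, the 8.6 platelet limits lie 200 to 800 times below the cut-off in 8.4, and the first hold lies 267 times below it. Because section 5.8.1 adopts Appendix 1 for interrupting study drug, the literal effect is that the temporary hold for immune thrombocytopenia would not be triggered at counts that 8.4 already treats as severe.

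The reach is limited. The point concerns the temporary-hold guidance and leaves the primary endpoint, the sample size and the permanent-stop rules untouched. It deserves correction because it bears on subject safety and is cheap to put right.

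The conclusion rests on two assumptions: that the unitless platelet figure in 8.4 is per microlitre, inferred from its neutrophil limits, and that the text of 8.6 read here matches the printed page.

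**What to change.** Check item 8.6 against the guideline from which it was copied. Reconcile its units with item 8.4 and with the grading scale named in section 9.1.1, and reprint the four platelet limits with an explicit unit. The sponsor should confirm whether a factor of 1,000 was dropped. Which limits are right is for the sponsor to settle from the source; none is proposed here.

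It would also help to add a sentence in section 5.8.1 saying how grades in Appendix 1 relate to CTCAE v5.0 where the two could differ.

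The cost is four table cells and, if wanted, one sentence. Design, sample size and analysis do not change.

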8.7 Acquired hemophilia	
Definition: Disorder caused by the development of autoantibodies (inhibitors) directed against plasma coagulation factors	
Diagnostic work-up	
Full blood count to assess platelet number, fibrinogen, PT, PTT, INR; the typical finding in patients with acquired hemophilia A is a prolonged activated PTT with a normal PT	
MRI, CT, and ultrasonography may be indicated to localize, quantify, and serially monitor the location and response of bleeding	
Medication review to assess for alternative causes	
Determination of Bethesda unit level of inhibitor	
(continued on following page)	

Table 8. Management of Hematologic irAEs in Patients Treated With ICPIs (continued)	
